3.2 Rationale for study design, doses and control groups

This study has a controlled design allowing us to evaluate efficacy in two different esomeprazole treatment regimens in patients with co-diagnosed NERD and CG. The randomized design ensures the unbiased baseline characteristics of the subjects in the two groups. The open-label design is chosen because the duration of treatment and the treatment regimen in maintenance/ follow up phase are different in the two groups.

Based on Nexium® product package insert, for symptomatic treatment of GERD, the indicated dose is 20 mg once daily in patients without esophagitis. Once symptoms have resolved, subsequent symptom control can be achieved using an on demand regimen taking 20 mg once daily, when needed. 2007 China GERD consensus (Chinese Medical Association, 2007) recommends 8 weeks initial PPI treatment followed by personalized maintenance treatment for NERD patients. Therefore, esomeprazole 20 mg qd 8 weeks treatment followed by 24 weeks on-demand maintenance treatment is considered as NERD standard treatment in the present study. On the other hand, a lot of NERD patients are misdiagnosed as CG and treated irregularly in China clinical practice. Therefore, our study will not only evaluate the efficacy of 8 weeks treatment regimen, but also compare with 2 weeks treatment regimen.

According to 2006 Montreal definition (Vakil N et al 2006), NERD can be diagnosed on the basis of typical reflux symptoms. The newly published Diamond study (Jones R et al 2009) already demonstrated that GerdQ is a simple and effective symptom-based assessment tool for GERD diagnosis and management. Therefore, in the present study, GerdQ is not only used as diagnostic criteria for NERD in screening phase, but also an assessment tool for patients' symptom control status in maintenance/ follow-up phase.

4. SUBJECT SELECTION CRITERIA

Investigator(s) should keep a record, the subject screening log, of subjects who entered pre-study screening.

Each subject should meet all of the inclusion criteria and none of the exclusion criteria for this study. Under no circumstances can there be exceptions to this rule.

4.1 Inclusion criteria

For inclusion in the study subjects should fulfil the following criteria:

1. Provision of informed consent prior to any study specific procedures
2. Males and females aged 18 to 75 years

3. Heartburn and/or regurgitation symptoms last for at least 3 months
4. Endoscopic diagnosed as chronic gastritis (non-atrophic, and mild atrophic gastritis) within 2 weeks prior to randomization
5. GerdQ score ≥ 8

4.2 Exclusion criteria

Subjects should not enter the study if any of the following exclusion criteria are fulfilled:

1. Involvement in the planning and/or conduct of the study (applies to both AstraZeneca staff and/or staff at the study site)
2. Previous enrolment or randomisation in the present study
3. Participation in another clinical study with an investigational product during the last 3 month
4. Endoscopic visible reflux esophagitis, esophageal varices, Barrett's esophagus, malignancy or peptic ulcer
5. Patients with Hp positive result and are eager to take Hp eradication therapy will be excluded. If Hp positive, patients could take Hp eradication therapy after the study completion
6. Presence of any alarm features within the last 6 months, such as:
 - Unintentional weight loss >3 kg in the previous 3 months
 - Haematemesis, melaena or per-rectum blood loss in the previous year
 - Progressive dysphagia
 - Anaemia
 - Any other symptom suggestive of malignancy
7. Previous PPI or H₂RA therapy in the last 2 weeks before enrollment
8. Known intolerance/allergy to PPIs
9. History of esophageal, gastric or duodenal surgery

10. History of chronic condition (eg, osteoarthritis or rheumatoid arthritis) that requires long-term daily NSAID treatment
11. History of severe liver disease, including (but not limited to) cirrhosis and acute or chronic hepatitis
12. Liver enzymes (AST, ALT, or alkaline phosphatase) twice the upper limit of normal at baseline examination
13. Severe renal disease, including chronic renal disease or impaired renal function as manifested by any of the following: serum creatinine greater than 2.0 mg/dL or markedly abnormal urine protein at baseline examinations
14. Current or historical evidence (within 3 months) of the following diseases/conditions:
 - Signs and symptoms of gastric outlet obstruction (eg, abdominal distension, or multiple episodes of vomiting)
 - Zollinger-Ellison syndrome
 - Gastric or duodenal ulcers within the last 3 months
 - Pancreatitis
 - Severe cardiovascular, pulmonary disease or diabetes mellitus
 - Cerebral vascular disease, such as cerebral ischemia, infarction, hemorrhage, or embolus
15. Pregnancy or lactation (must have a negative urine pregnancy test at baseline). Women of childbearing potential must maintain effective contraception during the study period as judged by the investigator
16. Current treatment with phenytoin, warfarin (or other vitamin K antagonists), ketoconazole, itraconazole, cisapride and systemic corticosteroids
17. Any condition, which, in the opinion of the investigator, may interfere with the evaluation of the study objectives

Procedures for withdrawal of incorrectly enrolled subjects see Section 5.3.

5. STUDY CONDUCT

5.1 Restrictions during the study

PPI other than esomeprazole and H₂RA are not allowed during the study.

5.2 Subject enrolment and randomisation and initiation of investigational product

The Principal Investigator will:

1. Screen endoscope diagnosed CG patients with GerdQ questionnaire. The patients with $GerdQ \geq 8$ are potential subjects.
2. Obtain signed informed consent from the potential subject before any study specific procedures are performed.
3. Assign potential subject a unique enrolment number, beginning with 'E#'. .
4. Determine subject eligibility. See Sections [4.1](#) and [4.2](#)
5. Assign eligible subject unique randomisation code (subject number), beginning with '#'. The subjects will be randomized into two treatment groups, one is 8 weeks treatment regimen group, the other is 2 weeks treatment regimen group.

If a patient withdraws from participation in the study, then his/her enrolment/randomisation code cannot be reused.

5.2.1 Procedures for randomisation

The randomization will be performed by a computer equally for the two treatment regimens. Each centre will be provided with sealed treatment code envelopes corresponding to a list of patient randomization numbers. Randomization numbers will be assigned strictly sequentially as subjects become eligible for randomization. When a subject is allocated to a specified randomization number, the corresponding code envelope will be opened to identify the allocated treatment regimen (8 weeks or 2 weeks treatment regimen).

5.3 Procedures for handling subjects incorrectly enrolled or randomised or initiated on investigational product

Subjects who fail to meet the inclusion/exclusion criteria should not, under any circumstances, be enrolled or randomised. There can be no exceptions to this rule.

Where subjects that do not meet the selection criteria are randomised in error or incorrectly started on treatment, or where subjects subsequently fail to meet the study criteria post initiation, a discussion should occur between the AstraZeneca Study Delivery Team Physician and the Investigator regarding whether to continue or discontinue the subject from treatment.

The AstraZeneca Study Delivery Team Physician is to ensure all such decisions are appropriately documented. In situations where an agreement cannot be reached, the subject should have their study therapy stopped.

5.4 Blinding and procedures for unblinding the study

Blinding was not performed in this study (reasons given in Section 3.2).

5.5 Treatments

5.5.1 Identity of investigational product(s)

Investigational product	Dosage form and strength	Manufacturer
Esomeprazole	20 mg tablets	Astrazeneca AB, Sweden

All investigational products should be kept in a secure place under appropriate storage conditions. Esomeprazole is stored at room temperature, <30°C.

5.5.2 Doses and treatment regimens

Patients will be randomized into below two groups at the Visit 2.

8 weeks treatment regimen group:

Patients will receive 8 weeks esomeprazole 20 mg qd treatment, if symptom relieved (defined as no more than one day with mild symptoms of GERD during the previous 7 days), they will receive another 24 weeks on-demand maintenance treatment. The first drug dispensing during maintenance phase is the time of first relapse, which is defined as patients' symptom recur, go to consult investigators and need treatment in the opinion of investigator. The following on-demand drugs will be dispensed at Visit 5 and 6 if the first relapse happened before Visit 5. Patients will be instructed to "Take one tablet daily if needed for relief of your reflux symptoms for at least 3-5 days. Stop taking the tablets when your symptom is adequately controlled."

During 24 weeks on-demand maintenance treatment period, 14 tablets esomeprazole will be dispensed at each scheduled visit. If it is not enough before next scheduled visit, patients can

go to the study center to get extra drugs. If they do not have symptoms recur, and just come to get on-demand drugs, it is not considered as unscheduled visit.

2 weeks treatment regimen group:

Patients will receive 2 weeks esomeprazole 20 mg qd treatment, if symptom relieved, they will enter 24 weeks follow-up period. During the followed up period, if the patients' symptom recur and need treatment in the opinion of investigator, they will be given another 2-week esomeprazole 20 mg qd recurrent treatment. There is no limitation for the times of recurrent treatment in the 24-week follow up period.

Study medication should be taken once daily in the morning with a glass of water.

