1.4 Benefit/risk and ethical assessment

Preclinical bridging studies with esomeprazole reveal no particular hazard for humans based on conventional studies of repeated dose toxicity, genotoxicity, and toxicity to reproduction.

In the presence of any alarm symptom (eg, significant unintentional weight loss, recurrent vomiting, dysphagia, haematemesis or melaena) and when gastric ulcer is suspected or present, malignancy should be excluded, as treatment with esomeprazole may alleviate symptoms and delay diagnosis.

Patients on on-demand treatment should be instructed to contact their physician if their symptoms change in character. When prescribing esomeprazole for on demand therapy, the implications for interactions with other pharmaceuticals, due to fluctuating plasma concentrations of esomeprazole should be considered. In non-steroidal anti-inflammatory drugs (NSAID) treated risk patients, subsequent symptom control using on demand treatment is not recommended.

Global randomized, controlled trials (BU-NEG-0005 study) in patients with NERD have shown that esomeprazole 20mg qd taken on demand after 4 weeks initial treatment is an effective and cost-saving treatment regimen in the long-term management of NERD. However, we do not have any local data in Chinese population for the symptom control rate with this cost- effective treatment regimen. On the other hand, a lot of NERD patients are mis-diagnosed as CG and treated irregularly in clinical practice in China. Our current study

will not only provide efficacy data for NERD standard treatment (8 weeks treatment regimen) in Chinese population, but also compare with 2 weeks treatment regimen.

Although one group of NERD patients will receive 2 weeks treatment regimen in this study, we mimic real clinical practice how more than half of NERD patients are treated, and patients will receive another 2 weeks esomeprazole recurrent treatment if they feel symptom recur and go to see physicians during 24 weeks follow-up. There is no limitation for the times of recurrent treatment in the 24-week follow up period.

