3.1 Overall study design and flow chart

This is a randomized, open-label design. The study is designed to be naturalistic in accordance with how patients are treated in clinical practice in China.

Patients with endoscope diagnosed chronic gastritis (non- atrophic, and mild atrophic gastritis) and GerdQ ≥ 8 will be randomized into two groups.

One group is the 8 weeks treatment regimen group, patients will receive esomeprazole 20 mg qd treatment for 8 weeks, the patients whose symptom relieved (defined as no more than one day with mild symptoms of GERD during the previous 7 days) will have another 24 weeks on-demand maintenance treatment. The 8 weeks treatment regimen is the NERD standard treatment recommended by China GERD consensus ([Chinese Medical Association 2007](#)).

[figure not shown]
The second group is the 2 weeks treatment regimen group, patients will receive 2 weeks esomeprazole 20 mg qd treatment, if symptom relieved, they will enter 24 weeks follow-up period. During the followed up period, if the patients' symptoms recur and need treatment in the opinion of investigator, they will be given another 2-week esomeprazole 20 mg qd recurrent treatment, and no limitation for the times of recurrent treatment in 24 weeks follow up period.

The patients whose symptom not relieved after 8 weeks treatment in 8 weeks treatment regimen group or 2 weeks treatment in 2 weeks treatment regimen group will be withdrawn from the study and treated according to clinical routines.

There are three scheduled visits (8, 16 and 24 weeks) in 24 weeks' on-demand maintenance treatment/ follow up period. Any unscheduled visits are guided by the patient's symptom recur, need for extra treatment, or the patients' need for medical consultation.

GerdQ will be assessed when the patients enter the study and at 8, 16 and 24 weeks' visit in maintenance treatment/ follow-up period to assess the symptom control in two groups. Controlled patients are defined as patients with all the items ≤ 1 in A and C category of GerdQ. The symptom control rate will be compared between two treatment regimen groups at the three scheduled visits (8, 16 and 24 weeks in 24 weeks' maintenance treatment/ follow-up period).

Figure 1 Study flow chart

* Only patients whose symptoms relieved after 8 weeks/ 2 weeks treatment will enter 24 weeks maintenance/ follow-up period.

Table 1 Study Plan 1 (Visits in 8 weeks/2 weeks treatment period)

	Pre-entry		8 weeks/ 2 weeks treatment		
	Visit 1 ^a	2	3	4	

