	Week -1	Week 0	Week 2	Week 8 ^b	
Inclusion & exclusion criteria	X	X			
Informed Consent	X				
Randomisation		X			
Medical history	X				
Demographic data	X				
Urine HCG ^c		X			
Physical examination	X				
Vital signs	X				
Laboratory measurement ^d	X				
Hp infection ^{d,e}	X				
Concomitant medication	X	X	X	X	
Drug dispensing		X	X ^b		
Drug accountability			X	X	
GerdQ assessment	X				
SAEs/ DAEs ^f assessment	X ^g →	X→	X→	X→	

^a Once informed consent given, baseline procedures may be completed within 1 week prior to treatment start.

^b Just for patients in 8 weeks treatment regimen group.

- ^c For women of child-bearing potential, a pregnancy test with a negative result must have been made before study.
- ^d Laboratory test results in the previous 2 weeks are acceptable, no need to repeat laboratory test at Visit 1.
- ^e Hp infection status diagnosed by ¹³C-urea breath test (UBT), rapid urease test or pathologic test.
- ^f Only SAEs and DAEs will be collected.
- ^g SAEs will be captured from time of signature of informed consent. DAEs will be captured from time of first dose of IP.

Table 2 Study Plan 2 (Visits in 24 weeks on-demand maintenance treatment/ follow-up period)

	24-week Maintenance treatment/ follow up			
	5 Week 8 ± 3d	6 Week 16 ± 3d	7 ^a Week 24 ± 3d	Unscheduled ^b
Concomitant medication	X	X	X	X
Drug dispensing	X ^c	X ^c		X
Drug accountability	X	X	X	X
GerdQ assessment	X	X	X	
Patient satisfaction	X	X	X	
SAEs/ DAEs ^d assessment	X→	X→	X	X

- ^a If a patient discontinues from the study prior to the Week 24 visit (study completion), every effort should be made to have the patient return for a clinic visit at the time of, or soon after discontinuation to complete all Final Visit procedures.
- ^b This includes all unscheduled visits carried out during maintenance treatment/ follow up period due to symptom recur and extra treatment needed. Total unscheduled visits will be compared between two treatment group.
- ^c Just for patients in 8 weeks treatment regimen group, only after the first relapse happened. If patients in CG group have symptom relapse at a scheduled visit, drugs will also be dispensed to them.
- ^d Only SAEs and DAEs will be collected.

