6.3.2 Derivation or calculation of outcome variable

Symptom control rate is calculated as the proportion of patients whose symptom controlled at the Week 8, 16 and 24 visits in maintenance treatment or follow-up phase. Controlled patients are defined as patients with all items ≤ 1 in A and C category of GerdQ.

Time to first relapse is defined as after 8 weeks / 2 weeks treatment, the time to the patients first come to see the investigator because of symptom recur, and need for treatment. The on-

demand drugs in the 8 weeks treatment regimen group will be dispensed after the first relapse. The average time to first relapse in the two groups will be compared.

Symptom relief is defined as patients with no more than one day mild symptoms of GERD during the previous 7 days. Symptom relief rate is calculated as the proportion of patients whose symptom relieved after 8 weeks and 2 weeks treatment.

Unscheduled hospital visit is calculated as the number of unscheduled hospital visit in 8 weeks treatment regimen and 2 weeks treatment regimen groups.

Patient satisfaction will be measured using a 7-point scale (completely satisfied-1; very satisfied-2; quite satisfied-3; satisfied-4; dissatisfied-5; very dissatisfied-6; completely dissatisfied-7). The patient will fill out the scale at Week 8, 16 and 24 visits in maintenance treatment or follow-up period. The proportion of patients satisfied (scores 1-4) or very satisfied (scores 1-2) will be calculated.

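### Time to first relapse (secondary) rests on an unblinded judgement with no symptom threshold, and no GerdQ is taken at the unscheduled visits where relapse is usually declared

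*Protocol*

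**What the plan says.** Time to first relapse is a secondary endpoint, estimated by Kaplan-Meier and compared by log-rank test (section 12.2.1; section 6.3.1 as amended).

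- **Event, 8-week arm (section 5.5.2):** "which is defined as patients' symptom recur, go to consult investigators and need treatment in the opinion of investigator".
- **Recurrence, 2-week arm (section 5.5.2):** a further course is given "if the patients' symptom recur and need treatment in the opinion of investigator".
- **Endpoint derivation (section 6.3.2, unchanged by Amendment 1):** "the time to the patients first come to see the investigator because of symptom recur, and need for treatment".
- **Blinding:** none (section 5.4). Section 3.2 explains: "The open-label design is chosen because the duration of treatment and the treatment regimen in maintenance/ follow up phase are different in the two groups". It does not discuss how outcomes are judged.
- **When the score is taken (section 3.1):** "GerdQ will be assessed when the patients enter the study and at 8, 16 and 24" weeks. Table 2 agrees: GerdQ is marked at Visits 5, 6 and 7, and the Unscheduled column has no mark.
- **Unscheduled visit (Table 2, footnote b):** "This includes all unscheduled visits carried out during maintenance treatment/ follow up period due to symptom recur and extra treatment needed".
- **Section 1.4, 2-week arm:** patients are treated again "if they feel symptom recur and go to see physicians". The investigator's opinion is not mentioned there.

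**The concern.** The protocol's other two symptom outcomes have explicit rules. Relief allows at most one day of mild symptoms in the previous seven, and control requires every A and C item of GerdQ to be 1 or lower. Relapse has no such rule. Two people who know the arm settle it: the patient decides to come, and the investigator decides that treatment is needed.

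Declaring relapse also has different consequences in the two arms. In the 8-week arm it opens the on-demand supply. In the 2-week arm it gives another two-week course, repeatable without limit. Sections 1.1 and 1.2 state in advance which regimen is expected to do better. A difference in threshold between the arms is therefore plausible, and the usual relapse visit is the one that leaves no symptom score behind. At stake is whether a log-rank result on this endpoint could be defended.

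**Working it through.** **1. The plan's own figures.** Section 12.3 concerns the primary endpoint: 66% v 86% controlled, 85 evaluable per arm, Fisher's exact test, two-sided 0.05. Exact enumeration gives 83.8% power, consistent with the stated figure of over 80%. The number to randomise is 170 / 0.70 / 0.80 = 303.6, consistent with about 300. These figures hold, but they do not bear on relapse. No power or event rate is stated for time to first relapse.

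**2. Is a score available when relapse is declared?**

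| Visit | GerdQ taken? | Used in the relapse definition? |
|---|---|---|
| Scheduled, weeks 8, 16, 24 | Yes | No |
| Unscheduled (recurrence, extra treatment needed) | No | No |

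Table 2, footnote c, allows for a relapse at a scheduled visit, so the missing score applies to unscheduled visits only. Concomitant medication, dispensing, accountability and SAEs/DAEs are recorded at unscheduled visits. They show what was given, not how often the patient had symptoms.

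**3. How sensitive is the log-rank test to unequal thresholds?** This is an illustration. Every input except the 85 and the 5% level is an assumption.

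- Symptoms recur at the same constant hazard in both arms, with 24 weeks of follow-up.
- p is the 24-week probability of a declared relapse in the 2-week arm, varied from 34% to 60%.
- q is the rate at which relapse is declared in the 8-week arm, as a fraction of the 2-week rate. q < 1 was chosen for illustration; the problem is the same in the other direction.
- 4,000 simulated trials per setting, two-sided 5% log-rank test.

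| q | Significant, 85 per arm | Significant, 105 per arm |
|---|---|---|
| 1.0 | about 5% | about 5% |
| 0.9 | 7–9% | 7–8% |
| 0.8 | 12–20% | 15–23% |
| 0.7 | 24–40% | 30–46% |
| 0.5 | 62–87% | 72–93% |

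The 105 is 150 × 0.70, the number relieved per arm before dropout.

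Hand check for q = 0.8 with 85 per arm. The expected number of declared relapses in the assumed scenario (not a forecast for this trial) is D = 85 × [p + 1 − (1 − p)^q], and the shift of the test statistic is |ln q| × √D / 2.

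- p = 0.34: D = 85 × (0.34 + 0.283) = 52.9; shift = 0.223 × 7.27 / 2 = 0.811; Φ(0.811 − 1.96) + Φ(−0.811 − 1.96) = 0.125 + 0.003 = 12.8% (simulated 12.1%).
- p = 0.60: D = 85 × (0.60 + 0.520) = 95.2; shift = 0.223 × 9.76 / 2 = 1.088; Φ(1.088 − 1.96) + Φ(−1.088 − 1.96) = 0.192 + 0.001 = 19.3% (simulated 20.3%).

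**The case against.** The event is not investigator opinion alone. Symptoms must recur and the patient must come in. Section 5.5.2 uses the same investigator condition for both arms, and neither arm holds on-demand tablets before the first relapse. The trial is described as naturalistic, and time to a consultation that needs treatment suits that aim. All of this stands, and it is a reason to keep the declared event as the endpoint. It is no reason to leave symptoms unrecorded at that visit. A SAP cannot help, because it cannot analyse a score that was not collected.

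A second objection is that GerdQ is completed by a patient who also knows the arm, and that it counts days, not severity. A patient who comes promptly after one bad day may score 1 and remain unconfirmed. This also stands, and it limits the score to a supporting role.

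Third, section 1.4 is a benefit/risk narrative, and the operative sections (3.1 and 5.5.2) agree with each other. The mismatch is therefore minor, but the two statements still need reconciling.

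A reader might go further and take 34% and 14% as the relapse rates, as complements of the 66% and 86% control rates, and multiply by 85 to count affected events. The documents do not support this. The synopsis says that the control rates were based on relapse in an earlier study, but control at week 24 is a status at one time point. A patient who relapsed early, was treated and is controlled at week 24 counts as controlled. A patient can also be uncontrolled at week 24 without having consulted. In addition, 85 is the evaluable number after dropout, not the number relieved.

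**Conclusion.** The point holds as a gap in measurement on a secondary endpoint. Relapse has no symptom threshold, nobody is blinded, and the usual relapse visit has no symptom score, so unequal thresholds between the arms could be neither detected nor ruled out. Amendment 1 leaves this in place.

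Its actual size is unknown. The table above shows only that modest inequality would matter: a 20% to 30% relative difference in declaration takes the false-positive rate from 5% to about 12–40% with 85 per arm, given constant hazards and an assumed 24-week relapse probability of 34% to 60%. The fraction q is freely chosen, and nothing in the documents estimates it. A reader might infer that the comparison is biased, or biased towards the 8-week regimen because the sponsor expects it to win. The protocol shows neither. The primary endpoint, GerdQ control at week 24, does not use the relapse definition. This is a cheap improvement, not a fault that undermines the trial.

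**What to change.** 1. Add GerdQ to the Unscheduled column of Table 2, completed by the patient before the consultation. It should be filled in however the visit ends, so that visits where relapse is not declared also carry a score.
2. Keep the investigator-declared event as the endpoint. Add a sensitivity analysis of time to first relapse with at least one A or C item scoring 2 or more, meaning not controlled by the protocol's own rule. This assumes the four answer boxes in Appendix C are coded 0 to 3 in order. State how a declared but unconfirmed visit is handled, and tabulate by arm the share of declared relapses that are confirmed.
3. State the limits: the patient is unblinded, GerdQ counts days and not severity, and relapses before the change have only the declared event.
4. Reconcile the retreatment trigger in section 1.4 with that in section 5.5.2. The treatment decision itself is not touched by this proposal.

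Cost: a six-item form already in use, a few minutes per unscheduled visit, one addition to the CRF and one extra survival analysis.

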1.2 Research hypothesis

For endoscope diagnosed CG patients with typical reflux symptoms, 8 weeks treatment regimen can provide better symptom control, followed by higher patient satisfaction and less hospital visit.

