In the 8 weeks treatment regimen group, to compare the symptom relief rate after 2 weeks and 8 weeks treatment	In the 8 weeks treatment regimen group, the symptom relief rate after 2 weeks and 8 weeks treatment (Symptoms relief are defined as no more than one day with mild symptoms of GERD during the previous 7 days). (ITT, ITT-PP)	Summary statistics (number and percentage of patients in each category).
To compare the number of unscheduled hospital visit between the two different treatment regimen groups.	The number of unscheduled hospital visit in the two treatment regimen groups. (MITT and MITT-PP)	Descriptive statistics (number, mean, median, standard deviation, minimum and maximum). Treatment group comparison of unscheduled hospital visit, two sample t-test.

Objective	Summary variables for analysis (including timepoint and population)	Statistical analysis methods or presentation of data
To measure patient satisfaction in the two different treatment regimen groups.	The proportion of patients satisfied (scores 1-4) or very satisfied (scores 1-2) in the two different treatment regimen groups after 8, 16 and 24 weeks on-demand maintenance treatment/ follow up. Patient satisfaction will be measured 7-point scale (completely satisfied-1; very satisfied-2; quite satisfied-3; satisfied-4; dissatisfied-5; very dissatisfied-6; completely dissatisfied-7) (MITT and MITT-PP)	Summary statistics (number and percentage of patients in each category). Treatment group comparison of proportion of patients satisfied and very satisfied, Fisher's Exact test.

Reason for Amendment:

Relief rate is to evaluate the efficacy of initial 8 week or 2 week treatment, and symptom control rate is to evaluate the efficacy of 24 weeks maintenance treatment/follow up period. Now success rate is added to evaluate the efficacy of whole treatment regimen, it is the combination of relief and control.

Persons who initiated the Amendment:

Study physician

Section of protocol affected:

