Symptom relief is defined as patients with no more than one day mild symptoms of GERD during the previous 7 days. Symptom relief rate is calculated as the proportion of patients whose symptom relieved after 8 weeks and 2 weeks treatment.

Unscheduled hospital visit is calculated as the number of unscheduled hospital visit in 8 weeks treatment regimen and 2 weeks treatment regimen groups.

Patient satisfaction will be measured using a 7-point scale (completely satisfied-1; very satisfied-2; quite satisfied-3; satisfied-4; dissatisfied-5; very dissatisfied-6; completely dissatisfied-7). The patient will fill out the scale at Week 8, 16 and 24 visits in maintenance treatment or follow-up period. The proportion of patients satisfied (scores 1-4) or very satisfied (scores 1-2) will be calculated.

Reason for Amendment:

Relief rate is to evaluate the efficacy of initial 8 week or 2 week treatment, and symptom control rate is to evaluate the efficacy of 24 weeks maintenance treatment/follow up period. Now success rate is added to evaluate the efficacy of whole treatment regimen, it is the combination of relief and control.

Section of protocol affected:

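### Tablet pickups without recurrence are left out of the unscheduled-visit count; only the 8-week arm can make them, the judgement is unblinded, and no symptom or reason item is scheduled to support it

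*Protocol*

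**What the plan says.** The research hypothesis in section 1.2 is that "8 weeks treatment regimen can provide better symptom control, followed by higher patient satisfaction and less hospital visit". The efficacy table in 6.3.1, as revised by Amendment 1, lists the number of unscheduled hospital visits as a secondary variable in MITT and MITT-PP, with "Treatment group comparison of unscheduled hospital visit, two sample t-test".

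Four places bear on what is counted:

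- **Section 6.3.2** (unchanged by Amendment 1): "Unscheduled hospital visit is calculated as the number of unscheduled hospital visit in 8 weeks treatment regimen and 2 weeks treatment regimen groups".
- **Section 3.1, text:** unscheduled visits are guided by "symptom recur, need for extra treatment", or a need for medical consultation.
- **Section 3.1, Table 2, footnote b:** the column covers "unscheduled visits carried out during maintenance treatment/ follow up period due to symptom recur and extra treatment needed". The footnote adds that the total is what the arms are compared on.
- **Section 5.5.2, 8-week arm:** patients who run short between scheduled visits may come for more tablets, and "If they do not have symptoms recur, and just come to get on-demand drugs, it is not considered as unscheduled visit".

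In the 2-week arm, further drug follows only a recurrence that the investigator thinks needs treatment; then "they will be given another 2-week esomeprazole 20 mg qd recurrent treatment". Section 5.4 states that there is no blinding.

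**The concern.** A trip to the centre for more tablets can be left out of the count, and only one arm can make such a trip. A 2-week patient who needs more drug must attend with a recurrence. That attendance counts unless it falls on a scheduled visit. An 8-week patient who needs more drug may be classed as a pickup and not counted.

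Whether symptoms have recurred is judged by someone who knows the arm, and the schedule provides nothing to check the judgement against later. Each omitted trip lowers the 8-week count, which is the direction the study hopes to show. A difference in unscheduled visits could then be read as fewer trips to hospital when part of it comes from the counting rule.

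**Working it through.** **1. The protocol's own figures.** It gives no SD, visit rate or pickup rate for this endpoint, so there is no stated figure to reproduce. The sample-size statement in 12.3 concerns the primary endpoint only. It reproduces (Fisher's exact power 83.8% with 85 per arm at 66% against 86%; 170 / 0.70 / 0.80 = 303.6, about 300) and does not depend on this point.

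**2. The rules side by side.**

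| Unplanned attendance | 3.1 text | Table 2, footnote b | 5.5.2 |
|---|---|---|---|
| Recurrence, treatment needed | counts | counts | counts |
| 8-week patient, tablets only, no recurrence | can count (need for extra treatment) | does not count | does not count |
| Consultation only, no treatment | counts | does not count if read literally | silent |

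The text of 3.1 is the outlier. Footnote b and 5.5.2 agree on tablet pickups. Section 6.3.2 does not choose between them, and the consultation-only visit is unsettled.

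**3. What is scheduled.** The unscheduled column of Table 2 marks concomitant medication, drug dispensing, drug accountability and SAEs/DAEs. GerdQ is not marked, and no item covers symptoms or the reason for attending. An attendance that 5.5.2 says is not an unscheduled visit has no column, and 5.7.1 does not list it among the dispensing occasions.

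**4. Who can make a pickup.** Only 8-week patients who have already had a first relapse, because on-demand drug is first dispensed then (5.5.2). Visit 5 to Visit 6 is 16 - 8 = 8 weeks, or 56 days. The supply per scheduled visit covers 28 / 56 = 50% of days since Amendment 1 (14 / 56 = 25% before), so a patient must use tablets on more than half the days to run short.

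**5. Illustration of the exclusion.** This measures what leaving pickups out can do to the test. It does not measure the effect of the mismatched wording.

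- Patients per arm in MITT: 150 x 0.70 = 105 (randomised number and response rate from 12.3, the same rate assumed in both arms).
- Assume equal total trips in the two arms and a common SD.
- Mean difference at the 5% line = t(0.975, 208) x SD x sqrt(2/105) = 1.971 x 0.138 x SD = 0.272 x SD.
- Excluded pickups in the whole 8-week arm = 0.272 x SD x 105:

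| Assumed SD (visits) | Difference per patient | Pickups, 105 per arm | Pickups, 85 per arm |
|---|---|---|---|
| 0.5 | 0.136 | 14 | 13 |
| 1 | 0.272 | 29 | 26 |
| 2 | 0.544 | 57 | 52 |

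In a simulation with 105 per arm and trips Poisson with mean 1 per patient (assumed), leaving out 0%, 10%, 20% or 30% of 8-week trips gave p < 0.05 in about 5%, 12%, 33% and 65% of trials with equal trips. The true share of omitted trips is not known.

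**The case against.** The strongest reply is that a rule exists. Section 5.5.2 addresses exactly these patients, footnote b agrees with it and is the text tied to the comparison, and the text of 3.1 only describes why patients attend. This stands. A reader might infer that the protocol has no rule for tablet returns; it has one.

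A reader might also argue that the exclusion has no settled meaning. Tablets are taken on the instruction "Take one tablet daily if needed for relief of your reflux symptoms", so anyone who has used them up has had symptoms since the last supply. But on that reading almost every pickup follows a recurrence and the exclusion covers hardly anyone. The reason given in Amendment 1 treats running out and recurrence as separate events, with recurrence as what brought the patient in. Symptoms at the time of attendance is the sensible reading, although the sentence gives no time frame.

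It is also fair to reply that dispensing is not unrecorded. Section 5.7 requires the administration of all medication to be entered in the CRF, and 5.7.1 requires tablet counts and documented amounts. That nothing is recorded at a pickup would be an inference. The narrower fact is that Table 2 has no column for it and no reason or symptom item by which to classify an unplanned attendance.

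Finally, pickups may be rare. According to Amendment 1, some patients who ran out did not come for more and attended only once symptoms recurred, and those attendances count. The supply was then doubled. This limits the size. It leaves unchanged that the exclusion falls on one arm and rests on an unblinded judgement without a scheduled record.

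**Conclusion.** The point holds as a cheap improvement of low severity. Followed as written, the protocol removes some trips to the centre from a tested count in the 8-week arm only, on an unblinded judgement for which no symptom or reason item is scheduled. The description in 3.1 does not match footnote b or 5.5.2, and 6.3.2 settles nothing. The comparison can lean towards the 8-week regimen.

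The size is unknown and may be small. The figures of 14 to 57 pickups rest on an assumed SD of 0.5 to 2 visits, equal trips in the arms and 105 patients per arm. They show what the exclusion could do, not what it did. A reader might infer from them that a significant difference in visits would be an artefact; the documents give no pickup rate and do not support that. The primary endpoint, its power and the sample size are not affected.

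**What to change.** - **One definition in 6.3.2.** Replace the circular sentence with a definition of an unscheduled visit. Keep the 5.5.2 exclusion, judged on symptoms at the time of attendance, and state whether a consultation-only visit counts. Align 3.1 and footnote b of Table 2 with it.
- **A record at every unplanned attendance, pickups included:** date, reason for attendance, current symptom status and tablets dispensed.
- **One extra results row.** Report unscheduled visits plus pickups by arm, in MITT and MITT-PP, beside the main count, so that a reader can see whether the result depends on the exclusion.

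No new symptom threshold should be added to the exclusion. For example, requiring at most one day of mild symptoms in the past 7 days would redefine a secondary endpoint while the study is running, and it could turn many pickups into visits, because patients who run short are frequent users.

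The cost is a few CRF fields and one table row. For pickups already made, only dispensing records may exist, so their symptom status may be missing.
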